7.3 Withdrawal from the study

Patients are free to withdraw from the study at any time (IP and assessments) without prejudice to further treatment.

Patients who withdraw consent for further participation in the study will not receive any further IP or further study observation, with the exception of follow-up for survival, which will continue until the end of the study unless the patient or his/her parent(s)/legally authorized representative(s) has expressly withdrawn their consent to survival follow-up. Note that the patient may be offered additional tests or tapering of treatment to withdraw safely.

A patient or his/her parent(s)/legally authorized representative(s) who withdraws consent will always be asked about the reason(s) for withdrawal and the presence of any AE. The Investigator will follow-up AEs outside of the clinical study.

If a patient or his/her parent(s)/legally authorized representative(s) withdraws consent, they will be specifically asked if they are withdrawing consent to:

- All further participation in the study including any further follow-up (eg, survival contact telephone calls)
- Withdrawal to the use of any samples (see Section 8.8.7).

8. STUDY ASSESSMENTS AND PROCEDURES

Study procedures and their timing are summarized in the SoA. The schedule for study procedures for the dose-finding and dose-expansion phases are presented in [Table 1](#) and [Table 2](#) respectively. The schedule of study procedures for patients who have discontinued all study treatments (durvalumab monotherapy or durvalumab and tremelimumab combination therapy) in the dose-finding or the dose-expansion are presented in [Table 3](#).

The Investigator will ensure that data are recorded on the electronic CRF. The Web Based Data Capture system will be used for data collection and query handling.

The Investigator ensures the accuracy, completeness, legibility, and timeliness of the data recorded and of the provision of answers to data queries according to the Clinical Study Agreement. The Investigator will sign the completed electronic CRFs. A copy of the completed electronic CRFs will be archived at the study site.

Immediate safety concerns should be discussed with the Sponsor or designee immediately upon occurrence or awareness to determine if the patient should continue or discontinue study treatment.

Adherence to the study design requirements, including those specified in the SoA, is essential and required for study conduct. All screening evaluations must be completed and reviewed to confirm that potential patients meet all eligibility criteria. The Investigator will maintain a screening log to record details of all patients screened and to confirm eligibility or record reasons for screening failure, as applicable.

Procedures conducted as part of the patient's routine clinical management (eg, blood count and imaging assessments) and obtained before signing of the ICF may be utilized for screening or baseline purposes provided the procedures met the protocol-specified criteria and were performed within the time frame defined in the SoA.

Enrollment/screening period

All screening evaluations must be completed and reviewed to confirm that potential patients meet all eligibility criteria. The screening procedures (presented in [Table 1](#) and [Table 2](#)) will be completed within 28 days of signing the ICF and before durvalumab infusion on Cycle 1 Day 1 (radiological assessments to be completed within 21 days before on Cycle 1 Day 1). The Investigator will maintain a screening log to record details of all patients screened and to confirm eligibility or record reasons for screening failure, as applicable. At screening, consenting patients are assessed to ensure that they meet eligibility criteria (Sections [5.1](#) and [5.2](#)). Patients who do not meet these criteria must not be started on treatment. Patients will be considered to be in the screening period until all screening visit assessments are completed and eligibility is confirmed. Patients will be considered to be in the dose-finding period after the first dose of durvalumab has been administered.

Dose-finding phase

Descriptions of the procedures for this period are included in the SoA for the dose-finding phase of the study (Table 1).

Patients will receive durvalumab monotherapy on Cycle 1 Day 1 and will be closely monitored for 28 days for safety and tolerability (DLT observational period 1) attending clinic visits on Days 8 and 15. Starting on Cycle 2, patients will receive durvalumab + tremelimumab in combination on Day 1 and attend clinic visits on Days 8 and 15. Cycle 2 Day 1 to Day 28 is the second DLT observational period; the total DLT observational period is 56 days or 2 cycles. Starting at Cycle 3, patients will have a scheduled visit only on Day 1 of the treatment cycle. From Cycle 6 onwards, patients will receive durvalumab monotherapy until progression.

Dose-expansion phase

Once a RP2D has been confirmed, patients will be recruited to the dose-expansion phase and will follow the procedures for this period in Table 2. All patients will receive durvalumab + tremelimumab in combination on Day 1 of Cycles 1, 2, 3, and 4. From Cycle 5, patients will receive durvalumab monotherapy until progression.

Off-treatment follow-up

Patients should be discontinued from study treatment if any discontinuation criteria are fulfilled, (Section 7.1). The assessments to be carried out during follow-up are detailed in Table 3. Any SAEs and/or non-serious AEs ongoing at the time of treatment discontinuation or which have occurred during the follow-up period must be followed up (in accordance with Section 8.3.3). Appropriate safety evaluations should be repeated and/or additional tests performed at any time when clinically indicated, or at the discretion of the Investigator, until resolution, unless, in the Investigator's opinion, the condition is unlikely to resolve due to the patient's underlying disease. If the patient is lost to follow-up, then this should be noted in the CRF. Survival will be collected every 2 months for all patients (Section 8.1.2).

Volume of blood and prioritization of laboratory sampling

For a patient weighing less than 6 kg, the following parameters for blood volume collection should apply:

- Maximum blood volume in 24 hours: 2 mL/kg.
- Maximum blood volume in 8 weeks: 8 mL/kg.

The total volume of blood that will be drawn as maximum per day (Cycle 1 Day 1) and for the 60-day period encompassing Cycle 1 and Cycle 2 has been carefully assessed across the weight range 6 kg to 55 kg to stay below the World Health Organisation blood limit guidelines (Table 18; Howie 2011). Pediatric tubes/microcontainers should be used, whenever possible, for blood collection. If there is any difficulty obtaining specimens or the local blood volume limits are met at any one time for any patient, the order of sampling priority should be followed as

outlined below. Safety labs, as listed in the prioritization schedule, include chemistry, hematology (see [Table 19](#) and [Table 20](#)) and thyroid stimulating hormone.

Sampling and prioritization order for Cycles 1 through 3

Dose-finding phase:

- ≤ 6 kg: Safety >PK durvalumab/tremelimumab >ADA durvalumab/tremelimumab
CCI [REDACTED].
- >6 kg to ≤ 20 kg: Safety >PK durvalumab/tremelimumab >ADA
durvalumab/tremelimumab CCI [REDACTED].
- >20 kg: Safety >PK durvalumab/tremelimumab >CCI [REDACTED] >ADA
durvalumab/tremelimumab CCI [REDACTED].

Dose-expansion phase:

- ≤ 6 kg: Safety >PK durvalumab/tremelimumab >ADA durvalumab/tremelimumab
CCI [REDACTED].
- >6 kg to ≤ 20 kg: Safety >PK durvalumab/tremelimumab >ADA
durvalumab/tremelimumab CCI [REDACTED]
[REDACTED] >vaccine titer.
- >20 kg: Safety >PK durvalumab/tremelimumab >ADA durvalumab/tremelimumab
CCI [REDACTED] >vaccine titer CCI [REDACTED].

Table 18 Volume of blood to be collected (by weight and including World Health Organisation limits)

Total blood volume (TBV): 80 mL/kg^a					
Weight (kg)	6	10	20	35	55
TBV (mL)	480	800	1600	2800	4400
WHO limits per 24 hours: 1–5% TBV Sick kids: 3.8% TBV			WHO limits per 8 weeks: up to 10% TBV		
Dose-finding phase					
Max volume (mL) per 24 hours (% TBV)	12.5 (2.6)	12.5 (1.6)	20.5 (1.3)	20.5 (0.73)	20.5 (0.47)
Volume (mL) per 8 weeks (%TBV)	32 (6.6)	32 (4)	56 (3.5)	56 (2)	56 (1.27)
Volume (mL) from Cycle 3 until progression	Safety labs (chemistry/hematology/TSH) at each cycle: 4 mL Research labs (according to Schedule of Activities): up to 14.5 mL (+3.5 mL for tumor markers with each tumor assessment) between Cycles 3 and 12				
EOT (mL)	4	4	4	4	4
Dose-expansion phase					
Max volume (mL) per 24 hours (% TBV)	20 (2.9)	20 (2.5)	28 (1.7)	28 (1)	28 (0.63)
Volume (mL) per 8 weeks (%TBV)	38 (7.9)	40.5 (5)	64.5 (4)	64.5 (2.3)	64.5 (1.5)
Volume (mL) from Cycle 3 until progression	Safety labs (chemistry/hematology/TSH) at each cycle: 4 mL Research labs (according to Schedule of Activities): up to 6 mL (+3.5 mL for tumor markers with each tumor assessment) between Cycles 3 and 12				
EOT (mL)	4	7.5	7.5	7.5	7.5

^a WHO range: 75–80 mL/kg (beyond neonatal period); maximum of 105 mL/kg from birth to 1 month.
EOT end of treatment; Max maximum; TBV total blood volume; TSH thyroid-stimulating hormone; WHO World Health Organisation.

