8.2.2 Clinical safety laboratory assessments

Blood and urine samples for determination of clinical chemistry, hematology, and urinalysis will be taken at the times indicated in the assessment schedules and as clinically indicated (see the SoAs).

Clinical laboratory safety tests, including serum pregnancy tests, will be performed in a licensed clinical laboratory according to local standard procedures. Sample tubes and sample sizes may vary depending on the laboratory method used and routine practice at the site. Pregnancy tests (performed only on female patients of childbearing potential) may be performed at the site using a licensed test (urine or serum pregnancy test). Abnormal clinically significant laboratory results should be repeated as soon as possible (preferably within 24 to 48 hours).

Additional safety samples may be collected if clinically indicated at the discretion of the Investigator. The date, time of collection, and results (values, units, and reference ranges) will be recorded on the appropriate CRF.

The laboratory variables to be measured are presented in Table 19 (clinical chemistry), Table 20 (hematology), and Table 21 (urinalysis).

Other safety tests to be performed at screening include assessment for hepatitis B surface antigen, hepatitis C antibodies, and HIV antibodies.

The following laboratory variables will be measured:

Table 19 Clinical chemistry

Albumin	Lipase ^b
Alkaline phosphatase	Magnesium ^c
ALT ^a	Potassium
Amylase ^b	Sodium
AST ^a	Total bilirubin ^a
Bicarbonate ^c	Total protein
Calcium	TSH ^e
Chloride ^c	T3 free ^f (reflex)
Creatinine ^d	T4 free ^f (reflex)
Gamma glutamyltransferase ^e	Urea or blood urea nitrogen, depending on local practice
Glucose	
Lactate dehydrogenase	

^a Tests for ALT, AST, alkaline phosphatase, and TBL must be conducted and assessed concurrently. If TBL is $\geq 2 \times$ upper limit of normal (and no evidence of Gilbert's syndrome), then fractionate into direct and indirect bilirubin.

^b It is preferable that both amylase and lipase parameters are assessed. For sites where only 1 of these parameters is routinely measured, either lipase or amylase is acceptable.

^c Bicarbonate (where available), chloride, creatinine clearance, gamma glutamyltransferase, magnesium testing are to be performed at baseline, on Day 1 (unless all screening laboratory clinical chemistry assessments are performed within 3 days prior to Day 1), and if clinically indicated.

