8.8 Biomarkers

By participating in this study, the patient's parent(s)/legally authorized representative(s) consents to the collection and use of donated biological samples as described here.

CCI [REDACTED] will be evaluated in enrolled patients CCI [REDACTED]
[REDACTED]
[REDACTED] tumor requirements are briefly described in Section 8.8.1.

CCI [REDACTED]
in Section 8.8.3. CCI [REDACTED] are described in this section. Samples will be obtained according to the assessment schedules provided in the SoAs.

Details for collection, volumes, storage, and shipment of biologic samples are presented in a separate Laboratory Manual.

All samples collected for biomarker analyses will be stored at the study site, a reference laboratory, or at AstraZeneca facilities and may be used for subsequent research relevant to CCI [REDACTED] to immunotherapy.

The results may be pooled with biomarker data from other durvalumab/tremelimumab studies to evaluate CCI [REDACTED] across indications and to compare results in monotherapy versus combination settings.

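### Table 18: the dose-expansion 24-hour maximum at 6 kg pairs 20 mL with 2.9% of blood volume, and the two figures cannot both be right

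*Protocol*

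**What the plan says.** Protocol Section 8, under the heading on blood volume and sampling priority, states that the maximum draw on one day (Cycle 1 Day 1) and the total over the 60 days of Cycles 1 and 2 were "carefully assessed across the weight range 6 kg to 55 kg to stay below the World Health Organisation blood limit guidelines". Table 18 is cited in support.

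Table 18 is built on "Total blood volume (TBV): 80 mL/kg", which gives 480 mL at 6 kg. Its 24-hour limits entry shows two figures: a general range of 1–5% of total blood volume, and "Sick kids: 3.8% TBV". In the dose-expansion block, the 24-hour maximum is 20 mL (2.9%) at 6 kg and 20 mL (2.5%) at 10 kg.

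Other provisions bear on small children:

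- Below 6 kg a separate cap applies: "Maximum blood volume in 24 hours: 2 mL/kg".
- A priority order for samples takes effect if specimens are hard to obtain or if "local blood volume limits are met at any one time for any patient".
- Section 8.9 omits vaccine-titer samples in the smallest patients to respect blood volume limits.
- Section 8.8 says "Details for collection, volumes, storage, and shipment of biologic samples are presented in a separate Laboratory Manual".
- For safety tests, Section 8.2.2 says "Sample tubes and sample sizes may vary depending on the laboratory method used and routine practice at the site".

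**The concern.** The volume and the percentage in a cell of this table should be two expressions of one quantity. At 6 kg in the dose-expansion phase they are not. This is the lowest weight in the table, in the phase with the larger single-day draw, on the day when most blood is taken.

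The two halves lead to different conclusions. Someone reading the percentage sees a draw comfortably below the 3.8% line. Someone reading the volume, and dividing by the 480 mL printed above it, sees a draw above that line. The table is the evidence offered for the Section 8 assurance, so at this weight it does not show whether the lower of its two limit figures is met.

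**Working it through.** **Inputs, all from Table 18.** Total blood volume (TBV) is 80 mL/kg. The footnote also gives 75 mL/kg as the lower end of the range beyond the neonatal period, and 105 mL/kg as a maximum from birth to 1 month.

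**Formula.** Percentage = 100 × volume / (mL per kg × weight).

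**Reproducing the table at 80 mL/kg** (volume in mL: printed % / recomputed %):

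| Row | 6 kg | 10 kg | 20 kg | 35 kg | 55 kg |
|---|---|---|---|---|---|
| Dose-finding, 24 h | 12.5: 2.6 / 2.60 | 12.5: 1.6 / 1.56 | 20.5: 1.3 / 1.28 | 20.5: 0.73 / 0.732 | 20.5: 0.47 / 0.466 |
| Dose-finding, 8 weeks | 32: 6.6 / 6.67 | 32: 4 / 4.00 | 56: 3.5 / 3.50 | 56: 2 / 2.00 | 56: 1.27 / 1.273 |
| Dose-expansion, 24 h | **20: 2.9 / 4.17** | 20: 2.5 / 2.50 | 28: 1.7 / 1.75 | 28: 1 / 1.00 | 28: 0.63 / 0.636 |
| Dose-expansion, 8 weeks | 38: 7.9 / 7.92 | 40.5: 5 / 5.06 | 64.5: 4 / 4.03 | 64.5: 2.3 / 2.30 | 64.5: 1.5 / 1.47 |

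Nineteen cells agree to rounding or truncation, within 0.07 percentage points. One does not: 20/480 = 4.17%, which is 1.27 points above the printed 2.9%.

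**Can another blood volume explain it?** No.

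- At 75 mL/kg: 20/450 = 4.44%.
- At 105 mL/kg: 20/630 = 3.17%.
- To get 2.9% from 20 mL, TBV would have to be 20/0.029 = 690 mL, or about 115 mL/kg.

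**What volume fits 2.9%?** 0.029 × 480 = 13.9 mL. Volumes from 13.68 to 14.16 mL round to 2.9% (2.85% to 2.95% of 480 mL).

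**Against the printed limits at 6 kg.** The 3.8% line is 0.038 × 480 = 18.2 mL, and 5% is 24 mL. So 20 mL lies between the two, and 14 mL is below both.

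**Which half is wrong?** The visible evidence points in two directions.

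- *Towards a volume below 20 mL.* Vaccine titers are dropped in the smallest patients (Section 8.9). Table 2 schedules titers at Cycle 1 Day 1 and at the end-of-treatment visit. The dose-expansion end-of-treatment volume is 4 mL at 6 kg and 7.5 mL at 10 kg, whereas dose-finding, which takes no titers, has 4 mL at every weight. If the 3.5 mL difference is the titer sample (an inference), leaving it out on Day 1 gives 20 − 3.5 = 16.5 mL, or 3.4% of 480 mL.
- *Against a full drop to 14 mL.* The 8-week total at 6 kg is only 40.5 − 38 = 2.5 mL below the 10 kg total. A 14 mL draw would be 6 mL lower on Day 1 alone, so the 6 kg patient would have to give 3.5 mL more than the 10 kg patient on the other days.

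Neither reading fits every neighbouring cell.

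**The case against.** The strongest reply is that this is a slip in one cell, probably a volume carried over from the next column, and that nothing should be built on it. Titers are omitted in the smallest patients and the 6 kg end-of-treatment volume is lower, so the same 20 mL at 6 kg and 10 kg looks doubtful. Part of the sample list for patients of 6 kg or less is redacted, and the composition that would reconcile the cell may lie there. Even at 4.2% the draw is inside the 1–5% range. Sites also have pediatric tubes, the Laboratory Manual, a 2 mL/kg cap below 6 kg, and a priority order that sheds research samples.

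Most of this stands. A volume below 20 mL is plausible, and a reader's inability to settle the matter from the public text is not in itself a gap in the plan. But the reply leaves the printed mismatch in place, and none of the safeguards is a 3.8% limit: the priority order responds to sampling difficulty or local limits.

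A reader might go further and infer that 6 kg children are to be bled beyond a WHO limit. The documents do not support that. It requires both that 20 mL is the true volume and that the 3.8% line, not the 1–5% range, governs these patients. The protocol establishes neither. Nor may a reader assume the reverse, that 2.9% is right and the draw is 14 mL, because the 8-week totals do not bear that out.

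**Conclusion.** The cell is wrong as written: at 480 mL, 20 mL is 4.2%, and 2.9% is about 14 mL. This rests only on the table's own blood volume and holds under every alternative in its footnote. Damage in the text extraction is unlikely, since the row has five values in order and the other four match their columns.

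The size is one cell of twenty, in the dose-expansion phase, at the lowest tabulated weight. It matters because the cell supports a safety statement, and its two halves fall on opposite sides of the 18.2 mL line. No breach of a limit is shown, and no endpoint or analysis is affected. Severity is minor.

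A new per-kilogram cap for children just above 6 kg does not follow from this error. It would assume that 20 mL is correct, that it applies between the 6 kg and 10 kg columns, and that 3.8% governs.

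**What to change.** Check the Cycle 1 Day 1 sample list for a 6 kg dose-expansion patient against the Laboratory Manual, then print a volume and percentage that agree.

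- If the true volume is below 20 mL, correct the volume and, unless it is about 14 mL, the percentage too.
- If the true volume is 20 mL, print 4.2% and do one of two things. Either drop the lowest-priority research sample at that weight, under the existing order, so that the draw is 18.2 mL or less; or amend the Section 8 statement to say that it relies on the 1–5% range.

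The cost is one table cell and one document check. In the second case it is also either one sentence or the loss of a low-priority research sample at that weight.

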8.1 Efficacy assessments

Efficacy assessments of ORR, duration of response (DoR), DCR, and PFS will be derived (by AstraZeneca) using the response criteria defined below. Overall survival will also be assessed for each individual patient.

Tumor assessments will be done in accordance with the type of tumor: NB ([Appendix F](#)), other solid tumors ([Appendix E](#)).

Radiological assessments will be made following routine clinical practice procedures during screening and then every 8 weeks (relative to the date of Cycle 1 Day 1), until radiological progression. For patients who achieve an objective response (CR, PR) or stable disease and for whom the response is still evident at 12 months, subsequent tumor assessments are to occur every 16 weeks. Unscheduled assessments can be performed at any time during the study, as clinically indicated, based on signs and symptoms. Disease progression requires confirmation, the confirmatory scan should occur preferably at the next scheduled visit and no earlier than 4 weeks after the initial assessment of PD in the absence of clinically significant deterioration. Treatment will continue between the initial assessment of progression and confirmation for progression.

Tumor assessments will be made during screening/baseline and at regular (follow-up) intervals during study treatment. Pelvic imaging is recommended only when primary or metastatic disease in the pelvic region is likely. Any other areas of disease involvement should be additionally imaged based on the signs and symptoms of individual patients. It is important to follow the tumor assessment schedule as closely as possible (refer to the SoAs). If an unscheduled assessment is performed (eg, to investigate clinical signs/symptoms of progression) and the patient has not progressed, every attempt should be made to perform the subsequent assessments at the next scheduled visit. Treatment continues until clinical progression/deterioration or confirmed radiological progression, and scanning/tumor assessments continue throughout treatment until radiological progression plus an additional follow-up scan (if clinically feasible).

Screening/Baseline imaging should be performed no more than 21 days before start of study treatment, and ideally should be performed as close as possible to and prior to the start of study treatment. Definitions of lesions, methods of assessments and response types are defined in [Appendix F](#) for NB, [Appendix E](#) for other solid tumors (RECIST 1.1)

8.1.1 Central reading of scans

All images, including unscheduled visit scans, will be collected on an ongoing basis and sent to an AstraZeneca appointed contract research organization (CRO) for quality control check (QCC). Guidelines for image acquisition, de-identification, storage at the investigative site as source data and transfer to the imaging CRO will be provided in a separate document.

A blinded independent central review (BICR) of images will be performed at the discretion of AstraZeneca. Results of these independent reviews will not be communicated to Investigators, and results of Investigator radiological assessments will not be shared with the central reviewers. The management of patients will be based in part upon the results of the radiological assessment conducted by the Investigator. Further details of the BICR will be documented in the Independent Review Charter, (also referred to as ‘Imaging Charter’).

8.1.2 Survival assessments

Assessments for survival must be made 30 days, 2 months, 3 months, 4 months, and every 2 months following treatment discontinuation (Table 3). Survival information may be obtained via telephone contact with the patient or the patient's family, or by contact with the patient's current physician. The details of first and subsequent therapies for cancer, after discontinuation of treatment, will be collected.

In addition, patients on treatment or in survival follow-up will be contacted following the DCO for survival analyses to provide complete survival data. These contacts should generally occur within 7 days of the DCO.

